### **11.1.2 Last observation carried forward (LOCF)**

If no measurement is available at a time point, the last post-baseline measurement prior to the specific time-point will be used instead for analysis. Unless otherwise specified, if a patient initiates rescue medication, the last value taken on or before the first rescue will be used for analysis.

### **11.1.3 3-item clinical benefit endpoint**

As one of the two primary efficacy endpoints, it is defined as:

- an absolute drop of 0.5% or more from baseline HbA1c, and
- a relative drop of 3% or more from baseline for total body weight, and
- an absolute drop of 3 mmHg or more from baseline in seated systolic blood pressure.

The proportion of patients who meet this definition at week 24 will be analyzed. If no measurement for a patient is available at this time point for one or more of the 3 criteria, the LOCF rule will be applied to each missing value, followed by derivation of the 3-item endpoint. However, if a patient initiates rescue for glycaemic or blood pressure control prior to week 24, the patient will be classified as not meeting the definition of the 3-item clinical benefit endpoint regardless of the actual Week 24 or LOCF values obtained.

## **11.2 Calculation or derivation of safety variable(s)**

### **11.2.1 Other significant adverse events (OAE)**

During the evaluation of the AE data, an AstraZeneca medically qualified expert will review the list of AEs that were not reported as SAEs and DAEs. Based on the expert's judgement, significant adverse events of particular clinical importance may, after consultation with the Global Patient Safety Physician, be considered OAEs and reported as such in the Clinical Study Report. A similar review of laboratory/vital signs/ECG data will be performed for identification of OAEs.

Examples of these are marked haematological and other laboratory abnormalities, and certain events that lead to intervention (other than those already classified as serious), dose reduction or significant additional treatment.

### **11.2.2 Other safety variables**

The safety evaluations will include analyses of AEs, laboratory parameters, ECG, vital signs (pulse and BP), orthostatic BP, hypoglycaemic events, calculated creatinine clearance, estimated GFR (eGFR) and physical examination. The analysis of safety will be based on the safety analysis set. Safety data gained during the 24-week double-blind treatment period, the

28-week and the 52-week extension periods and the 3-week safety follow-up period will be evaluated. Safety variables will be summarized descriptively. CV events will be analyzed in conjunction with CV events observed in other Phase II and Phase III dapagliflozin studies and the combined results will be reported elsewhere.

The Cockcroft-Gault formula will be used to calculate creatinine clearance.

Males:

$$\text{Creatinine clearance (mL/min)} = \frac{\text{Weight (kg)} \times (140 - \text{Age})}{72 \times \text{serum creatinine (mg/dL)}}$$

Females:

$$\text{Creatinine clearance (mL/min)} = \frac{\text{Weight (kg)} \times (140 - \text{Age})}{72 \times \text{serum creatinine (mg/dL)}} \times 0.85$$

The MDRD equation will be used to calculate eGFR.

The mean of the 3 BP measurements will be computed by AstraZeneca for each position for each patient at each visit.

BMI will be computed by AstraZeneca ( $\text{BMI} = \text{weight} / \text{height}^2$ , where weight is measured in kg, and height in metres).

Patients reporting at least one episode of hypoglycaemia between baseline and week 24 will be tabulated using counts and proportions.

### **11.3 Calculation or derivation of patient reported outcome variables**

#### **EuroQol (EQ-5D)**

The respondent rates his/her current health state on the EQ VAS by drawing a line from the box marked "your health state today" to the appropriate point on the EQ VAS. A three-digit number between 000 and 100 is read off the thermometer, from the exact point where the line crosses the scale, for example, 046 or 098. This is the EQ VAS score. In order to achieve comparable results, it is necessary to adhere to the standard text and instructions and layout of EQ VAS.

The EQ-5D index includes five dimensions and each dimension has three levels: no problem, some problem and severe problem. Therefore, altogether there are 243 health states defined. A utility weight is assigned to each health state. Utility weights are elicited from general population surveys that used one of the available direct utility assessment methods.

The responses are straightforward to code and record. There is one response for each dimension, such that:

- level 1 (no problem) is coded as a '1'
- level 2 (some problem) is coded as a '2'
- level 3 (severe problem) is coded as a '3'

For comparative purposes, it is recommended that:

- missing response is coded as a '9'
- ambiguous response is coded as an '8'

#### **11.4 Calculation or derivation of pharmacokinetic variables (Not applicable)**

#### **11.5 Calculation or derivation of pharmacodynamic variable(s) (Not applicable)**

#### **11.6 Calculation or derivation of pharmacogenetic variables**

The number of patients that will agree to participate in the genetic research is unknown. It is therefore not possible to establish whether sufficient data will be collected to allow a formal statistical evaluation or whether only descriptive statistics will be generated. A statistical analysis plan will be prepared where appropriate.

#### **11.7 Calculation or derivation of health economic variables (Not applicable)**

### **12. STATISTICAL METHODS AND SAMPLE SIZE DETERMINATION BY ASTRAZENECA**

A comprehensive Statistical Analysis Plan (SAP) will be prepared before unblinding of the data.

#### **12.1 Description of analysis sets**

The evaluation of efficacy will be performed for the full analysis set as outlined below. The primary efficacy variables and selected secondary variables will also be analyzed using the

per-protocol analysis set if more than 10% of the patients in any treatment group in the full analysis set are excluded from the per-protocol analysis set.

The primary analysis will be based on the full analysis set using the last observation carried forward approach (LOCF).

The analysis of safety will be based on the safety analysis set.

A detailed description of analysis sets is given below. The decision to include or exclude patients from each analysis set will be performed in a blind data review prior to unblinding. A summary of the number of patients per analysis set will be given and reasons for exclusion of a patient from an analysis set will be listed.

### **12.1.1 Efficacy analysis set**

#### **12.1.1.1 Full analysis set**

The full analysis set will include all randomised patients (as randomised) who received at least one dose of study medication during the 24-week double-blind short-term treatment period who have a non-missing baseline value and at least one post-baseline value for at least one efficacy variable to be analyzed at week 24. The intention-to-treat principle will be preserved despite the exclusion of patients who took no study medication, as the decision of whether or not to begin treatment during the randomised treatment period could not be influenced by knowledge of the assigned treatment. Where appropriate, missing data will be replaced using the last observation carried forward (LOCF) approach.

#### **12.1.1.2 Per-protocol analysis set**

The per-protocol analysis set is a subset of the full analysis set consisting of patients who do not violate the terms of the protocol which may affect the primary efficacy endpoints significantly. All decisions to exclude patients from the full analysis set to create the per-protocol analysis set will be made prior to the unblinding of the study.

### **12.1.2 Safety analysis set**

The safety analysis set will include all patients who received at least one dose of randomised study medication and who provide any safety records. Patients who were dispensed the wrong randomised treatment (ie, those randomised to dapagliflozin 10 mg but actually given placebo, or vice versa) will be counted in the treatment group for which they received medication. Where appropriate, missing data will be replaced using the last observation carried forward (LOCF) approach.

## **12.2 Methods of statistical analyses**

### **12.2.1 Analysis of the 24-week double-blind short-term treatment period**

The two primary objectives of this study are to show superiority of dapagliflozin versus placebo in terms of (1) change in HbA1c from baseline to week 24 and (2) likelihood of meeting all criteria of the 3-item clinical benefit composite at week 24. These objectives will

also be assessed in the overall study population and separately for each of two strata: patients less than 65 years of age and patients 65 years of age or older.

For the first primary efficacy variable, the following null hypothesis H01 related to each age stratum and the two strata combined will be tested against the alternative hypothesis HA1:

$$H01: \quad \mu_T - \mu_P \geq 0,$$

$$HA1: \quad \mu_T - \mu_P < 0,$$

where  $\mu_T$  denotes the mean absolute change in HbA1c from baseline to week 24 in the group of patients treated with dapagliflozin (test medication, T) and  $\mu_P$  the corresponding mean absolute change in the group of patients treated with placebo (placebo, P).

Similarly, for the second primary efficacy variable, the following null hypothesis H02 related to each age stratum and the two strata combined will be tested against the alternative hypothesis HA2:

$$H02: \quad \pi_T - \pi_P \leq 0,$$

$$HA2: \quad \pi_T - \pi_P > 0,$$

where  $\pi_T$  denotes the probability of meeting all criteria of the 3-item clinical benefit endpoint at week 24 in the group of patients treated with dapagliflozin (test medication, T) and  $\pi_P$  the corresponding probability in the group of patients treated with placebo (placebo, P). Four key secondary variables have been identified:

1. Absolute change in seated SBP from baseline to week 8
2. Relative change (%) in total body weight from baseline to week 24
3. Absolute change in seated SBP from baseline to week 24
4. Proportion of patients with a baseline BMI  $\geq 27$  kg/m^2 with a reduction of 5% or more in body weight from baseline to week 24.

A hierarchical testing procedure will be used to control the Type I error rate across the two primary and four key secondary endpoints, both in the overall population as well as within individual age strata. Initially, a Bonferroni multiplicity correction will be applied to the two tests associated with the primary efficacy variables in the overall study population so that each variable will be tested at  $\alpha=0.025$  (2-sided). For a given primary efficacy variable, if the test for the overall population is statistically significant, an additional Bonferroni correction will be applied so that each test within age strata will be performed at  $\alpha=0.0125$  (2-sided); however, no within-age strata tests will be performed if the test for the overall population is not statistically significant.

After performing all applicable tests for primary efficacy variables, testing of key secondary variables will be performed in a fixed order sequence (see above). The testing sequence will be applied separately for the overall population and also for each of the two age strata. The alpha level used for each of the three testing streams will depend on the results of tests for the primary variables in the corresponding population:  $\alpha=0.05$  (2-sided) if both primary variables are statistically significant;  $\alpha=0.025$  (2-sided) if only one of the primary variables is statistically significant; or no testing if the none of the primary variables are statistically significant. Thus, alpha levels may differ among the three populations for the key secondary variables. Within each population, inference for hypothesis testing will stop at the first occurrence of a failed test, regardless of how testing has progressed in the other two populations.

The primary and secondary efficacy analyses will be based on the full analysis set. The primary efficacy variables and selected secondary variables will also be analyzed using the per-protocol analysis set if more than 10% of the patients in any treatment group in the full analysis set are excluded from the per-protocol analysis set.

The LOCF approach means that for all changes (or percent changes) from baseline to a specific time point post-baseline, analyses will be based on measurements available at that time point or the last post-baseline measurement prior to the time point, if no measurement is available at that time point. This LOCF approach will be used for all variables regardless of rescue medication. In addition, unless otherwise specified, if a patient initiates rescue medication (including an increase in dose of baseline medication), the last value taken on or before the first rescue dose will be used for analysis. This last rule will apply only to glycaemic and blood pressure variables (ie, rescue for glycaemic control applied only to analysis of HbA1c and FPG changes and responder derivations, whereas rescue for blood pressure control only applied to analysis of SBP and DBP changes and responder derivations).

The first primary efficacy variable, change in HbA1c from baseline to week 24, will be analyzed by an analysis of covariance (ANCOVA) model. When assessing the results overall, the model will include terms for treatment group, age-by-insulin use-by-time from most recent qualifying CV event group (8 levels), and baseline covariate. To help characterize the treatment effect, a secondary test for interaction between treatment group and age strata will be performed at the 0.10 level of significance; however, the results of this test will not alter the conclusion from the previously specified model since the effect of dapagliflozin versus placebo will be examined for each age stratum separately. When assessing the results within each age stratum, the ANCOVA model will include terms for treatment group, insulin use-by-time from most recent qualifying CV event group (4 levels), and baseline covariate. The ANCOVA model will be used to derive a least squares estimate of the treatment difference with 95% confidence interval and corresponding two-sided p-value. Further, two-sided 95% confidence intervals for the mean change within each treatment group will be calculated. The same method will be applied for analyzing other continuous efficacy variables. For variables analyzed as percent change from baseline, the ANCOVA model will apply to logarithm-transformed data and resulting least-squares means and confidence intervals back-transformed to provide estimates in the original scale.

The second primary efficacy variable, proportion of patients at week 24 who meet all criteria of a 3-item clinical benefit composite, will be analyzed by the Cochran-Mantel-Haenszel (CMH) method. When assessing the results overall, the CMH model will include age-by-insulin use-by-time from most recent qualifying CV event group as a strata variable. To help characterize the treatment effect, a secondary test for homogeneity of treatment effect between age strata will be performed at the 0.10 level of significance; however, the results of this test will not alter the conclusion of the previously specified model since the effect of dapagliflozin versus placebo will be examined in each age stratum separately. When assessing results within each age stratum, the CMH model will include insulin use-by-time from most recent qualifying CV event as a strata variable. The difference in response rates between dapagliflozin and placebo will be displayed along with a 95% confidence interval derived from asymptotic theory. P-values will be calculated from a chi-square test using the appropriate CMH model described above. If there are less than 5 responders on average by treatment group, an exact 95% confidence interval will instead be calculated along with the p-value from Fisher's exact test.

The proportion of patients achieving therapeutic glycaemic response, defined as HbA1c <7.0%, at week 24 will be analyzed using the methodology of [Zhang et al 2008](#) and [Tsiatis et al 2007](#) when there are at least 5 responders on average by treatment group. For proportion of responders, estimates, confidence intervals, and tests will be obtained using this methodology with adjustment for baseline HbA1c and age group. For each treatment group, the probability of response is first modelled using a logistic regression model with baseline HbA1c as the covariate. Treatment group estimates of response rate are then obtained by integrating each group's modelled probability of response over the observed distribution of baseline covariate (combined across groups). The difference in response rate between dapagliflozin and placebo will be displayed along with the 95% confidence intervals. P-values will be calculated (when applicable). When there are less than 5 responders on average by treatment group, the unadjusted proportions and difference between unadjusted proportions, exact 95% confidence interval, and p-values from the Fisher's exact test (when applicable) will be provided. Analyses will also be conducted separately within each age stratum. The same method will be applied for analyzing other proportions of patients achieving a pre-defined response derived from a single variable, including the key secondary variable proportion of patients with baseline BMI  $\geq 27$  kg/m^2 with a reduction of 5% or more in body weight from baseline to week 24.

Other discrete variables will be summarized by counts, proportions and corresponding two-sided 95% confidence intervals for each treatment group overall and, where appropriate, within each age stratum. Comparisons between treatments will be performed using two-sided Fisher's exact test, when applicable.

The time course of all continuous variables will be presented using standard descriptive summary statistics calculated at each scheduled measuring time point and the last individual measuring time point. Moreover, standard descriptive summary statistics will be calculated for the change (absolute or percent) from baseline to each scheduled measuring time point after baseline and the last individual measuring time point. Analyses by subgroups, including

the stratification factors of insulin use and time from qualifying CV event, will be defined in the SAP.

Due to the large number of centres and the expected low number of patients per centre it will not be appropriate to explore centre effects. Tables by region will be provided nevertheless in order to explore region effects. Region effects will be included in the statistical model in additional exploratory analyses if appropriate. Any pooling of countries with few patients in geographical clusters will be specified in the SAP before breaking the blind.

The mean change in EQ-5D and EQ VAS from baseline to each post-randomisation visit where evaluated will be summarized with descriptive statistics and point estimates with 95% confidence intervals. Full details of analysis methods for this instrument will be presented in the SAP.

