### 12.3 Determination of sample size

The sample size for this study was selected to be consistent with the research hypotheses as described in Section 1.2.

The study has two primary endpoints for which the overall probability of a Type 1 error (Family-wise error rate) will be strictly controlled at no more than 0.05 by testing each primary endpoint at a significance level  $\alpha=0.025$  in the overall population and 0.0125 within each age stratum. The sample size for this study is governed by the comparison with least power to achieve statistical significance; namely, for the within-age stratum comparison for the 3-item clinical benefit composite as explained below. Significance levels are expressed in terms of two-sided alternatives; however, all tests in practice will be performed against one-sided alternatives using one-half the significance levels reported here.

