From post-hoc results of a Phase III dapagliflozin study, when patients meeting entry criteria like those in this current study were selected, the proportion who successfully attained the 3-item clinical benefit composite endpoint after 24 weeks of treatment and who did not meet the rescue criteria in the current study was estimated to be 18.0% for dapagliflozin 10 mg (0% for placebo). The present trial seeks to detect a treatment difference over placebo of 15 percentage points within either age stratum with high statistical power (90%). Given patients will be randomised with equal probability to dapagliflozin or placebo, it follows that 362 patients (181 per group) will provide 90% power to detect a difference in responder rates of 25% versus 10% ( $\Delta=15\%$ ) within a given age stratum at a significance level  $\alpha=0.0125$  using a chi-square test. If 3.7% of randomised patients fail to qualify for inclusion in the full analysis set due to missing baseline and/or all post-randomization values for this primary endpoint, then a total of 376 randomized patients at minimum are required for each age stratum. Since it is permitted to randomize as few as 40% of the total patient population in one of the age strata, it follows that in order to ensure at least 90% power for the treatment comparison in the smaller age stratum, the larger age stratum must randomize 564 patients (60% of total). Therefore, with respect to the 3-item clinical benefit composite endpoint, 940 randomized patients in total are needed for the study. This sample size provides  $>99\%$  power to detect the same difference in the overall study population at a significance level  $\alpha=0.025$ .

With regard to the other primary efficacy variable, to detect a difference of 0.5% between dapagliflozin versus placebo for mean change in HbA1c from baseline to week 24, assuming a standard deviation (SD)  $\sigma=0.9\%$ , 181 evaluable patients (full analysis set) for each treatment group within a given age stratum would provide  $>99\%$  power for the analysis of each age stratum separately at a significance level  $\alpha=0.0125$  using a two-sample t-test. The estimate of

the SD for this calculation is based on data from the same study used to estimate proportion of patients attaining the 3-item clinical benefit noted above.

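### The extra halving to 0.0125 within age strata is not needed to hold the primary-family error at 0.05: behind the overall gate, 0.025 per stratum suffices and lifts the power of the sizing comparison from 90.0% to 93.9%

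*Supplement*

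**What the plan says.** Section 12.2.1 of the protocol (and the statistical methods in the synopsis) sets the levels in steps, all two-sided:

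- Overall population: "a Bonferroni multiplicity correction will be applied to the two tests associated with the primary efficacy variables in the overall study population", giving 0.025 for each variable.
- Gate: "no within-age strata tests will be performed if the test for the overall population is not statistically significant".
- Strata, once the gate is open: "an additional Bonferroni correction will be applied so that each test within age strata will be performed at" 0.0125.
- Key secondaries: a fixed sequence run separately in the overall population and in each stratum. The level is 0.05, 0.025 or no test, according to whether two, one or none of the primaries succeeded in that same population.

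Section 12.3 says the family-wise error for the two primaries "will be strictly controlled at no more than 0.05 by testing each primary endpoint" at 0.025 "in the overall population and 0.0125 within each age stratum". It adds: "Significance levels are expressed in terms of two-sided alternatives"; the tests are run one-sided at half those levels. On size it says "The sample size for this study is governed by the comparison with least power to achieve statistical significance", meaning the composite within an age stratum, and that "362 patients (181 per group) will provide 90% power to detect a difference in responder rates of 25% versus 10" per cent at 0.0125. No reason is given for using both the gate and the halving.

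**The concern.** A gate and a Bonferroni split are two ways of protecting the same pair of stratum tests. If the gate alone holds the stated bound, the split lowers power without lowering the maximum primary-family error. It does so in the comparison that fixed the trial's size. At stake are about four points of power for the composite in the smaller age stratum under the planning assumptions, and about two points if recruitment is even.

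**Working it through.** **Inputs.** From 12.2.1: 0.025 overall, 0.0125 per stratum, and the gate. From 12.3: 25% versus 10%, 181 per group, 1:1 allocation, 3.7% not in the full analysis set, and a smaller stratum of at least 40%. The planned 470 per stratum is in the synopsis.

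**Step 1: reproduce the plan's size.** Two-proportion formula with pooled variance under the null:

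n = [z(1−α/2)·√(2p̄q̄) + z(0.90)·√(p₁q₁+p₂q₂)]² / Δ²

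Here p̄ = 0.175, √(2p̄q̄) = √0.28875 = 0.5374, √(0.1875+0.09) = 0.5268 and Δ = 0.15. At α = 0.0125, z = 2.498 and n = (2.498×0.5374 + 1.282×0.5268)²/0.0225 = 180.9, so 181. Then 362/0.963 = 376 and 376/0.4 = 940. All three figures agree with 12.3.

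**Step 2: is the halving needed?** Take one primary variable and three nulls: overall, under 65, and 65 or over.

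- Both stratum nulls true: the overall null is then true. Any false claim must first pass the overall test, so the error is at most 0.025.
- Overall null true although one stratum benefits: the gate again caps the error at 0.025.
- Overall null false: at most one stratum null can be true, so a single test at 0.025 gives at most 0.025.

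This is closed testing with the overall test as the intersection test. Two variables give 2 × 0.025 = 0.05, the bound in 12.3. Without the gate, two strata at 0.025 would give 1 − 0.975² = 0.049 per variable, so it is the gate that makes the split unnecessary.

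Simulated two-sided family-wise error for one variable (4 million draws, null stratum holding 40% of the information):

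| True state | Strata at 0.0125 | Strata at 0.025 |
|---|---|---|
| Both strata null | 0.025 | 0.025 |
| One null, other stratum's expected z = 2 | 0.006 | 0.011 |
| One null, other z = 5 | 0.009 | 0.019 |
| One null, other z = 9 | 0.0125 | 0.025 |

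The maximum is 0.025 under both rules. A 50/50 split gives the same maximum. In the one-sided form, including effects of opposite sign, the error with strata at 0.025 is at most 0.0126 against a nominal 0.0125, which is within simulation error.

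**Step 3: power of the governing test.** Power = Φ{[Δ√n − z·√(2p̄q̄)]/√(p₁q₁+p₂q₂)}.

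- 181 per group: (2.018 − 1.342)/0.5268 = 1.283, or 90.0% at 0.0125. With z = 2.241: (2.018 − 1.204)/0.5268 = 1.545, or 93.9% at 0.025.
- 470 × 0.963 / 2 ≈ 226 per group: 95.8% at 0.0125 and 97.7% at 0.025.
- With the gate included and the same effect in both strata (181 and 272 per group, simulated): 90.7% and 94.4%. The gate is passed more than 99.99% of the time.
- With an effect in the smaller stratum only: 66.9% and 67.5%. Here the gate is the limit.

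**Step 4: what changes outside that bound.** Suppose both primaries are null in one stratum, with the gates open because of the other, and take the endpoints as independent. The chance of a false primary claim in the null stratum is 1 − 0.9875² = 2.5% now and 1 − 0.975² = 4.9% after the change.

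Add a first key secondary that is null everywhere, tested at 0.05 overall and in the other stratum (8.3% for at least one false rejection, equal strata, simulated). The wider-family error is then 1 − 0.9752×0.9167 = 10.6% now and 1 − 0.9506×0.9167, about 12.8% to 12.9%, after. If all primaries succeed in all three populations, the three key-secondary streams alone give about 11.5% under either rule.

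**The case against.** The strongest reply is that nothing here is wrong. The rule is valid, is stated consistently in the synopsis, 12.2.1 and 12.3, and its sample size is computed correctly. Asking for stronger evidence before an age-specific claim is a legitimate choice. That stands, and it makes this an optional refinement.

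The gain also depends on the scenario. It is largest at the 40% stratum and under two points at the planned split. HbA1c already has more than 99% power at 0.0125. At the prior rates quoted in 12.3 (18.0% versus 0%), composite power is above 99.9% at either level. If the effect is smaller than planned, the gain is larger: 20% versus 10%, an assumption made here, gives 57% and 67% at 181 per group.

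Three stronger inferences are tempting and should not be drawn.

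- A reader might infer that the change loses no error control at all. Section 12.2.1 declares a family that includes the four key secondaries in three populations, and stratum primary results set the level of the stratum's key-secondary stream. Step 4 shows the error over that family rising. It exceeds 0.05 already and the 0.0125 level does not cure this, but a claim of no loss holds only for the maximum over the primary tests.
- A reader might infer that about 820 patients would do in place of 940 (158 per group at 0.025; 316/0.963 ≈ 329; 329/0.4 ≈ 823). The version under review is the extension amendment, and planned recruitment was about 8 months from Q1 2010. On that timetable enrolment was over, so the saving was probably no longer available.
- A reader might take the 95% intervals in 12.2.1 as further support, since they match neither 0.025 nor 0.0125. They are given as estimates beside p-values, and nothing says significance is read from them. That is a separate reporting matter.

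**Conclusion.** The point holds as a cheap improvement limited to the primary tests. The halving to 0.0125 is not required for the 0.05 bound in 12.3. Removing it leaves the maximum primary-family error unchanged and raises composite power by 3.9 points at 181 per group, or 1.9 points at about 226 per group, for 25% versus 10%.

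The argument assumes that the overall stratified test is valid at its level and that the overall effect is null whenever both stratum effects are null. The stratified ANCOVA and CMH analyses meet the second condition. The price is that a null stratum's own error can double, from 0.0125 to 0.025 per variable, still inside the bound. The excess error of the key-secondary streams is a separate fault: it is present now and becomes somewhat larger after the change. The 10.6% and 12.8% to 12.9% figures are one illustrative case, not a maximum.

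**What to change.** Before the week-24 treatment codes are broken, amend the synopsis, 12.2.1 and 12.3:

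1. After a significant overall test at 0.025, test each age stratum at 0.025 two-sided (0.0125 in the one-sided form of 12.3). Say that the overall test is the intersection test of a closed procedure.
2. Restate composite power per stratum: 93.9% at 181 per group and 97.7% at about 226 per group.
3. State the price: a null stratum's error of up to 0.025 per variable, and the link to the key-secondary streams.
4. Either correct the key-secondary rule so that the three streams together respect 0.05, or confine the family-wise claim in 12.2.1 to the primary tests.

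Optionally, and as a separate matter, show 97.5% intervals beside the 95% ones for the primary variables (2.241/1.960, so 14% wider).

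The cost is wording, with no new data or patients, but it does relax a prespecified level. The documents do not show whether the week-24 lock had passed when this version was issued. If it had, the level should stay at 0.0125 and only the key-secondary claim needs attention.
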